a single day is 10.6 ml. Both amounts are well below the daily and sustained limits for blood collection in pediatric participants. These amounts will be even lower if microtainer collection of fingerstick samples is used and participants opt out of optional measures – the minimum required amount of blood drawn per participant over the complete course of the study is approximately 23.6 ml.

Protocol elements to mitigate risk include the exclusion of participants with known hypercalcemia, kidney stones, significant renal or parathyroid disease, and/or known diseases complicated by elevated 25(OH)D levels, including sarcoidosis, William Syndrome, and granulomatous diseases. Kidney stones are a known complication of hypercalcemia and hypercalcuria. Spot urine calcium/creatinine ratios will be monitored, and serum calcium levels will be obtained in any participant with elevated urine calcium/creatinine ratios.

---

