### 5.2 EXCLUSION CRITERIA

An individual who meets any of the following exclusion criteria will be excluded from participation in the study:

- Known diseases of calcium metabolism or the parathyroid
- History of renal insufficiency or kidney stones
- Known liver failure or history of abnormal liver function which is deemed by the site investigator to be clinically significant
- History of Williams syndrome, sarcoidosis, or granulomatous disease
- Active tuberculosis

- Spot urine calcium/creatinine ratio greater than 0.37 on 2 consecutive visits. If the ratio is greater than 0.37 on the first visit, this test must be repeated once - following adequate hydration, within 2 business days of the study team being notified of the initial lab results.
- Clinical evidence of rickets
- Taking supplemental vitamin D greater than 1000 IU per day
- Administration of an excluded medication (systemic glucocorticoids, drugs affecting calcium metabolism, drug affecting fat absorption) within 30 days prior to study enrollment – at screening (Visit 1) or at any time during the run-in period.
- Other medical issues that in the opinion of the investigator put the participant at risk or affect results of the study (e.g., fat malabsorption, cystic fibrosis, chronic lung disease of prematurity, congenital heart disease). Type 2 diabetes is not an exclusion criterion.
- Plans to move out of the study area in the next 9 months
- There is another child in the household enrolled in the study
- Plans for significant lifestyle changes in the next 9 months (significant dietary changes while enrolled in the study)
- Participants who are eligible for the run-in period will be ineligible for randomization if they do not demonstrate adherence to run-in procedures (return diary cards with a completion rate greater than or equal to 75%)

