## 7 STUDY INTERVENTION DISCONTINUATION AND PARTICIPANT DISCONTINUATION/WITHDRAWAL

### 7.1 DISCONTINUATION OF STUDY INTERVENTION

Discontinuation from taking vitamin D supplements does not mean discontinuation from the study, and remaining study procedures should be completed as indicated by the study protocol. If a clinically significant finding is identified such as an elevated urine calcium/creatinine ratio (greater than 0.37 on 2 measurements), elevated serum calcium level (greater than  $1.5 \times \text{ULN}$ ), or 25(OH)D level greater than 100 ng/ml after enrollment, the investigator or qualified designee will determine if any change in participant management is needed including discontinuation of vitamin D supplements. If a participant is discontinued from study drug (vitamin D supplement), he or she will be asked to complete any remaining study visits in order to assure his or her safety and for the sake of completeness of data collection. If a participant who has been asked to stop taking study drug terminates (for any reason) from the study, site coordinators will make reasonable efforts to complete a termination visit. The termination visit will include routine labs (safety labs at minimum) and a focused physical exam.

Rules for halting of study drug:

1. Spot urine calcium/creatinine ratio greater than 0.37 and subsequent serum calcium above  $1.5 \times \text{ULN}$  for the local laboratory. Because dehydration can artificially inflate the calcium/creatinine ratio, participants will be counseled on consuming adequate fluids throughout the study. Participants who have an elevated spot urine calcium/creatinine ratio will be asked to consume 6 to 8 eight-ounce glasses of water per day, and to return within 2 business days of the site team receiving initial lab results for a repeat calcium/creatinine ratio. If the repeat ratio is less than or equal to 0.37, study medication will be continued without interruption. If the ratio remains greater than 0.37, a local serum calcium level and local 25(OH)D will be checked. If the serum calcium is less than  $1.5 \times \text{ULN}$  and 25(OH)D is less than 100 ng/ml, the participant will continue study drug without interruption.

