If a participant develops elevated serum calcium greater than or equal to  $1.5 \times \text{ULN}$  or 25(OH)D level greater than 100 ng/ml by local lab, the participant will remain off study drug through the duration of the study, but will continue with all other study procedures. See Section 8.2 for further safety assessment information.

2. Any documented adverse event, which in the opinion of the site investigator warrants halting of study drug for participant safety.

If a participant develops elevated serum calcium greater than or equal to  $1.5 \times \text{ULN}$  or 25(OH)D level greater than 100 ng/ml, the participant will remain off study drug through the duration of the study, but will continue with all other study procedures.

The data to be collected at the time of study intervention discontinuation will include the following:

- Reason for discontinuation
- Serum 25(OH)D and serum calcium
- Urine calcium/creatinine ratio
- Concomitant medications (including vitamin D3 daily dose at screening in either individual supplement or as a part of a multivitamin)

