### 8.1.1.1 PROCEDURES BY STUDY VISIT

#### Screening Visit (Visit 1, Days -7 to -21)

The goal of this visit is to explain the study to potential participants, obtain informed consent/assent, and collect a brief medical history and laboratory studies to assess inclusion/exclusion criteria. After the Screening Visit is complete, eligible participants will begin the run-in period.

1. Inclusion/exclusion criteria will be reviewed. This will include age, BMI, asthma diagnosis, and ability to swallow pills, confounding medical conditions, and concomitant medications per protocol.
2. Informed consent/assent will be obtained for eligible participants (see Section 10.1.1). Once consent and assent have been obtained, the participant is enrolled in the study.
3. Demographic data will be recorded on the data collection form along with measured height and weight.
4. Medical history, including history of asthma exacerbations, will be obtained.
5. Participants (parent/guardian and child) will be asked to initial a form documenting whether they prefer to have this visit 1 blood sample taken from the child's arm or taken from a fingerstick.
6. Participants meeting all other eligibility criteria will have samples collected for local serum 25(OH) vitamin D assessment, urine pregnancy test (for female participants of child-bearing potential), and urine calcium/creatinine ratio.
7. Local safety measures (as described in Section 8.2) will be reviewed by the study coordinator to determine eligibility for continued enrollment. If any safety laboratory value exceeds the thresholds defined by protocol, the participant will be referred to the participant's primary care physician.
8. Diary cards, (without the line to record Vitamin D dosing), will be given to the participant and instructions for completion of the diary will be reviewed. These diary cards will have the questions about asthma control and symptoms and asthma medications, but will not have the questions about vitamin D dosing.

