## **8.2 SAFETY AND OTHER ASSESSMENTS**

Vitamin D is a very safe supplement with a large therapeutic index. Vitamin D sufficiency is considered to be greater than 30 ng/ml. Intoxication does not occur until serum 25(OH)D levels exceed 150 ng/ml (325 nmol/L).(85) However, most clinical laboratories consider 100 ng/ml to be the upper limit in order to maintain a wide safety margin. Reports of vitamin D toxicity are rare and virtually always related to faulty manufacturing or labeling of product such that individuals ingested hundreds to thousands of times the presumed dose.(86, 87) The consequence of vitamin D toxicity is hypercalcemia. Hypercalcemia only results when 25(OH)D concentrations have consistently been above 150-200 ng/ml (375-500 nmol/L).(85)

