#### 8.3.3.3 EXPECTEDNESS

The expectedness of an AE or suspected AR shall be determined according to the specified reference document containing safety information (e.g., most current product information or product label). Any AE that is not identified in nature, severity, or specificity in the current study drug reference document(s) (e.g., product information) is considered unexpected. Events that are mentioned in the product information as occurring with a class of drugs or as anticipated from the pharmacological properties of the drug, but not specifically mentioned as occurring with the particular drug in this study are considered unexpected.

Expected AEs that could occur in this study are: bruising related to venipuncture/fingerstick, pain related to venipuncture/fingerstick, increase in calcium in the blood or urine, kidney stones, accidental vitamin D poisoning (associated nausea and increased levels of calcium in the blood), increased urination, decreased appetite, increased fatigue, hypersensitivity to vitamin D, or hypercalcemia (only expected when vitamin D blood level is above 150-200 ng/mL, but the intervention will be stopped if level reaches 100 ng/mL).

If the capsule is ruptured or broken, the powder may cause the following: irritation or burning of the eyes, skin, or respiratory system (if inhaled).

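### Section 7.1 contradicts itself on whether the investigator or a fixed rule decides about stopping study drug, and its calcium and 25(OH)D limits do not agree at the boundary with each other or with sections 8.2 and 8.3.3.3

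*Combined protocol and SAP*

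**What the plan says.** Six statements in the protocol bear on stopping drug for calcium or 25(OH)D.

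- **7.1, opening paragraph.** A urine ratio above 0.37 on two measurements, serum calcium above 1.5 x ULN, or 25(OH)D above 100 ng/ml are given as examples of clinically significant findings. The investigator or a designee decides whether management changes, and discontinuation is one of the options.
- **7.1, rule 1, heading sentence.** Drug is halted for a ratio above 0.37 followed by serum calcium above 1.5 x ULN. 25(OH)D is not mentioned.
- **7.1, rule 1, body.** After a second high ratio, local serum calcium and 25(OH)D are measured. If calcium is below 1.5 x ULN "and 25(OH)D is less than 100 ng/ml, the participant will continue study drug without interruption".
- **7.1, paragraph that follows, repeated almost word for word under rule 2.** At serum calcium of 1.5 x ULN or more "or 25(OH)D level greater than 100 ng/ml by local lab, the participant will remain off study drug" for the rest of the study.
- **8.2.** Supplementation is stopped if calcium is above 1.5 x ULN or 25(OH)D is above 100 ng/ml.
- **8.3.3.3, list of expected events.** Hypercalcemia is expected only at high vitamin D levels, "but the intervention will be stopped if level reaches 100 ng/mL".

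Separately, rule 2 of 7.1 lets the site investigator halt drug for any adverse event judged to warrant it, and 7.2 allows withdrawal at the investigator's discretion.

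**The concern.** A halting rule should give one answer for each set of laboratory results. Here the same confirmed urine result is first left to the investigator and then tied to an instruction to go on dosing. The results at the other end of the scale are first left to the investigator and then tied to an instruction to stop. A site cannot tell which sentence governs. The limits carry different inequality signs in different places, so a result that lands on a limit has no single answer either.

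The stakes are consistency of participant management and, to a smaller degree, of the data. Whether a child is taken off drug affects the tabulation of withdrawals from treatment due to an adverse event (9.4.5). It also affects who is left out of the per-protocol population for not completing the 16-week regimen (9.5). Those classifications should depend on the child's results and not on which paragraph a site happened to apply.

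**Working it through.** No sample size, power or error rate is involved, so there is no statistical figure to reproduce. The check is to write each statement as a condition and evaluate all of them at the same results. Let C be serum calcium divided by the local ULN and D be 25(OH)D in ng/ml, in a child whose repeat urine ratio is above 0.37.

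| Statement | Condition | Action |
|---|---|---|
| 7.1 opening | confirmed ratio, or C > 1.5, or D > 100 | investigator decides |
| 7.1 rule 1 heading | C > 1.5 | halt |
| 7.1 rule 1 body | C < 1.5 and D < 100 | continue |
| 7.1 next paragraph | C ≥ 1.5 or D > 100 | off drug |
| 8.2 | C > 1.5 or D > 100 | stop |
| 8.3.3.3 | D ≥ 100 | stop |

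Evaluated at chosen values:

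| C | D | Continue | Halt or stop | Investigator decides |
|---|---|---|---|---|
| 1.01 or 1.49 | 60 or 99.9 | rule 1 body | none | yes (ratio) |
| 1.50 | 60 or 99.9 | none | 7.1 next paragraph only | yes (ratio) |
| 1.01 or 1.49 | 100 | none | 8.3.3.3 only | yes (ratio) |
| 1.01 or 1.49 | 100.1 | none | 7.1 next paragraph, 8.2, 8.3.3.3 | yes (ratio, D) |
| 1.51 | 60 or 99.9 | none | rule 1 heading, 7.1 next paragraph, 8.2 | yes (ratio, C) |

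From the rows:

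1. **Row 1, discretion against continuation.** The opening and the body of rule 1 both apply, and they differ. The overlap covers every calcium below 1.5 x ULN with D below 100, including calcium above the local ULN. That upper part is (1.5 − 1) x ULN = 0.5 x ULN wide. The documents give no ULN. If it is assumed to lie between 10.0 and 10.8 mg/dl, then 1.5 x ULN is 15.0 to 16.2 mg/dl and the width is 5.0 to 5.4 mg/dl. This only describes the range over which the two instructions compete; it is no comment on where the limit should be.
2. **Rows 4 and 5, discretion against a mandatory stop.** The opening leaves the decision open, while 7.1 and 8.2 require drug to be stopped.
3. **Row 2, calcium at equality.** One paragraph of 7.1 halts; the rule 1 heading and 8.2 do not.
4. **Row 3, 25(OH)D at equality.** Section 7.1 neither continues nor stops, and 8.2 does not stop; 8.3.3.3 does.
5. **Row 4, missing limb.** The rule 1 heading alone would not halt for 25(OH)D above 100 ng/ml, although the paragraph after it does.

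Reach: the rule is not specific to an arm, so all children on drug fall under it. In Part 2 that is up to 63 children, of whom 63 x 2/3 = 42 are in Cohort A. How many will have a confirmed high ratio, or a result in one of these rows, cannot be derived from the documents.

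**The case against.** The strongest reply is that investigators are not bound in practice. The opening of 7.1, rule 2 and the discretion in 7.2 all let them stop drug, and 8.3.3.3 lists raised calcium in blood or urine among the expected adverse events, so rule 2 can be reached. That stands, and it defeats one inference a reader might draw: that the protocol orders a child with raised calcium to stay on drug with no way out. The continue instruction also lapses once 25(OH)D is no longer below 100 ng/ml. But discretion is one side of the contradiction and does not resolve it.

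The boundary point is also narrow. At exactly 1.5 x ULN no sentence orders continuation, and the 8.3.3.3 wording is a parenthesis in a list of expected events. This limits the size of the point without removing it.

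Other stronger readings are not supported:

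- *The rule clashes with the entry criteria.* Section 5.2 excludes a "Spot urine calcium/creatinine ratio greater than 0.37 on 2 consecutive visits", 2.3.1 mentions exclusion for known hypercalcemia, and 8.1.1.1 refers children over a safety threshold to primary care. All three concern entry, and the referral is written for the screening visit only. Entry and stopping thresholds may differ, so this is at most an unexplained asymmetry.
- *The calcium limit is too lenient because 25(OH)D is acted on at its own upper limit.* The sentence in 8.2, "However, most clinical laboratories consider 100 ng/ml to be the upper limit in order to maintain a wide safety margin", is about 25(OH)D. Two analytes need not share a multiple of their limits, and where the calcium limit belongs is a clinical matter that the documents do not settle.
- *The safety results rest on a count of halted children.* The safety endpoints are adverse events and reactions, serious and non-serious (section 3). Raised calcium can be recorded as an event whether or not drug stops, and 8.3.4 requires events to be followed up.
- *This is the only laboratory halting rule.* Pregnancy also stops dosing (8.3.9), and urine pregnancy tests are scheduled.

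Section 8.2 adds that "Hypercalcemia only results when 25(OH)D concentrations have consistently been above 150-200 ng/ml". Raised calcium with 25(OH)D below 100 ng/ml is therefore a result its rationale does not foresee. This suggests the case is rare, and it also leaves the continue instruction unexplained there.

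**Conclusion.** The point holds as an internal contradiction in a safety halting rule. Section 7.1 assigns the same findings both to investigator judgement and to fixed instructions: continue in one range, stop in another. The limits disagree at calcium of exactly 1.5 x ULN and at 25(OH)D of exactly 100 ng/ml, and the rule 1 heading lacks the 25(OH)D limb found in its body. Two sites could each comply and act differently on the same result.

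The practical size is small. Few children are likely to be affected, though that is a judgement, because the documents give no rate of confirmed high ratios and no calcium ULN. The finding rests on the wording alone and does not depend on the assumed ULN. It does not show that any limit is wrong or that children are left without an override.

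**What to change.** Reconcile the opening of 7.1, the heading and body of rule 1, the paragraph after it and its repetition under rule 2 with 8.2 and 8.3.3.3. State the serum calcium limit and the 25(OH)D limit once each, with one operator each, and replace the other statements with cross-references. State whether investigator discretion or the fixed rule governs each finding. Include explicitly the case of a confirmed ratio above 0.37 with serum calcium above the local ULN but below the limit. The values and the actions are for the sponsor's clinicians and the DSMB; none is proposed here.

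The cost is an amendment to the wording, with the IRB review that any amendment requires, and a memo to sites. No new test is needed at the decision point, because serum calcium and 25(OH)D are already measured there. Depending on what the clinicians decide, the number of children whose dosing is reviewed or interrupted may change slightly; 7.1 already provides for their remaining visits to continue.

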## 7.2 PARTICIPANT DISCONTINUATION/WITHDRAWAL FROM THE STUDY

An investigator may discontinue or withdraw a participant from the study for the following reasons:

- Participant request. Participants are free to withdraw from participation in the study at any time for any reason.
- New medical issues that would make continuing in the study dangerous for the participant
- Pregnancy
- Significant study intervention non-compliance at the discretion of the site investigator
- At the discretion of the investigator

The reason for participant discontinuation or withdrawal from the study will be recorded. Participants who sign the informed consent form (i.e., are enrolled) but do not receive the study intervention may be replaced. Participants who sign the informed consent form, receive the study intervention, and subsequently withdraw or are withdrawn or discontinued from the study will not be replaced.

Participants who are withdrawn or who discontinue from the study for any reason are encouraged to return for final study procedures.

### 7.3 LOST TO FOLLOW-UP

A participant will be considered lost to follow-up if he or she fails to return for more than 2 consecutive scheduled visits and is unable to be contacted by the study site staff.

The following actions must be taken if a participant fails to return to the clinic for a required study visit:

- The site will attempt to contact the participant, reschedule the missed visit within 7 days of the missed visit, counsel the participant on the importance of maintaining the assigned visit schedule and ascertain if the participant wishes to continue in the study.
- Before a participant is deemed lost to follow-up, the investigator or designee will make every effort to regain contact with the participant (where possible, 3 telephone calls followed by a certified letter to the participant's last known mailing address or local equivalent methods). These contact attempts must be documented in the participant's medical record or study file.

Should the participant continue to be unreachable, he or she will be considered to have withdrawn from the study with a primary reason of lost to follow-up.

## 8 STUDY ASSESSMENTS AND PROCEDURES

### 8.1 STUDY ASSESSMENTS

#### 8.1.1 CLINICAL ASSESSMENTS

In the procedure sections below, it should be noted that PK blood samples can be collected by venipuncture or by fingerstick microtainer collection method. If the participant prefers venipuncture, then blood for inflammatory markers will also be drawn. Fingerstick is not an option for visits 2 and 6 since blood inflammatory markers must be assessed for those visits.

Note phone calls will be made at least biweekly (every 2 weeks) from research team to participant/family to promote adherence to medication.

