## 1 PROTOCOL SUMMARY

Title:	Vitamin D Oral Replacement in Asthma (VDORA1)
Study Description:	Multi-center, randomized, open-label, pharmacokinetic (PK) and safety study of oral vitamin D3 supplementation. This will be performed in two parts. The data from both parts will be combined for PK calculations.
Objectives:	
Study objective: The overall objective of the study is to determine the pharmacokinetics of Vitamin D supplementation in children who have asthma and are overweight or obese.
 
Part 1 objective: Identify dosing to use in Part 2 using PK analysis on a subset of participants.
 
Part 2 objective: Determine the effectiveness of a recommended 16-week dosing regimen to achieve a serum level of 25(OH)D greater than or equal to 40 ng/ml in vitamin D insufficient or deficient children who have asthma and are overweight or obese.
 
Safety objective: Assess the safety and tolerability of oral vitamin D3

	
Exploratory objectives:
 

1. Characterize selected inflammatory markers in children receiving vitamin D3 supplementation.

2. Characterize asthma symptoms in children receiving vitamin D3 supplementation.

3. Compare the proportion of participants randomized to receive an optimal dose of vitamin D based on PK data versus those who are exposed to standard of care doses that achieve serum 25(OH)D greater than or equal to 40 ng/ml.

Endpoints:	
Study endpoint: Pharmacokinetic analysis of vitamin D supplementation in children who have asthma and are overweight/obese.
 
Part 1 endpoint: Serum 25(OH)D will be evaluated at baseline and various times including post-dose elimination to determine preliminary PK analysis for the best dose for increasing vitamin D levels above 40 ng/ml in children with asthma who are overweight or obese.
 
Part 2 endpoint: Did participants in the Part 2 active dosing cohort achieve a serum 25(OH)D of greater than or equal to 40 ng/ml at 16 weeks?
 
Safety endpoints: Adverse events (AEs), serious adverse events (SAEs), adverse reactions (ARs), and serious adverse reactions (SARs)

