- f periodic communication may be via phone, text, or email as participant prefers. Communication will occur at least every other week in weeks without a study visit between Visits 2 and 6, and then contact will be made, minimally, during the week prior to each Follow-up Visit (visits 7, 8 and 9)
- g performed locally; if urine Ca++/Cr ratio is greater than 0.37 on repeat testing [after adequate hydration and within 2 business days of initial test], the patient will return for a local serum calcium and 25(OH)D. If urine Ca++/Cr sample is not obtained at the scheduled visit, the sample must be obtained within 2 business days. This is necessary because Ca++/Cr is a safety assessment.
- h leptin plus TNF $\alpha$ , IL-2, IL-6, IL-10, and IL-17 (cytokine panel). These will be drawn by venipuncture at baseline and Visit 6. If blood for vitamin D level is drawn by venipuncture (vs fingerstick) at other times, sufficient blood will be collected for inflammatory marker determination.
- i for participants having venipuncture (vs fingerstick) blood draw
- j local laboratory determination of serum 25(OH)D will be performed at week 28 (visit 9).
- k blood for central laboratory vitamin D determination can be collected by venipuncture or by fingerstick using a microtainer collection tube
- l an optional blood draw (fingerstick or venipuncture) can occur any time between week 1 and 3 (from day 7 to day 21, inclusive).

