### 2.3.3 ASSESSMENT OF POTENTIAL RISKS AND BENEFITS

All participants randomized will have vitamin D insufficiency and participation in this study will lead to appropriate supplementation. Benefits may be related to improved 25(OH)D level effects on bone health with a potential for a positive effect on asthma control. Risks of blood draws are minimal and not outside those encountered in daily living. We will provide the option for fingerstick collection of small volumes of blood for vitamin D level determination in order to lessen the anxiety of venipuncture in children. Risks will be mitigated by implementation of inclusion and exclusion criteria that decrease the chance of any hypercalcemia-associated problems and by monitoring urine calcium/creatinine ratios.

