## 3 OBJECTIVES AND ENDPOINTS

OBJECTIVES	ENDPOINTS	JUSTIFICATION FOR ENDPOINTS
Study		
The overall objective of the study is to determine the pharmacokinetics of vitamin D supplementation in children who have asthma and are overweight or obese.	Pharmacokinetic analysis of vitamin D supplementation in children who have asthma and are overweight or obese	PK characteristics of 25(OH)D following vitamin D3 supplementation are not known in this population.
Part 1		
Identify dosing to use in Part 2 using PK analysis on a subset of participants	Serum 25(OH)D will be evaluated at Baseline and various times including post-dose elimination to determine preliminary PK analysis for the best dose for increasing vitamin D levels above 40 ng/ml in children with asthma who are overweight or obese	PK characteristics of 25(OH)D following vitamin D3 supplementation are not known in this population.
Part 2		
Determine the effectiveness of a recommended 16-week dosing regimen to achieve a serum level of 25(OH)D greater than or equal to 40 ng/ml in vitamin D insufficient or deficient children who have asthma and are overweight or obese.	Did participants in the Part 2 active dosing cohort achieve a serum 25(OH)D of greater than or equal to 40 ng/ml at 16 weeks	Serum 25(OH)D level greater than or equal to 40 ng/ml has been implicated to be anti-inflammatory.

OBJECTIVES	ENDPOINTS	JUSTIFICATION FOR ENDPOINTS
Safety		
Assess the safety and tolerability of oral vitamin D3	Adverse events (AEs), serious adverse events (SAEs), adverse reactions (ARs), and serious adverse reactions (SARs)	Assessing safety is important to determining tolerability of vitamin D in this study population.
Exploratory		

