### **Study Visit 6 (Week 16, Day 112 [ $\pm 7$ ])**

1. Unused medication will be returned and the study coordinator will review the diary cards for dosing visits.
2. ACT (or c-ACT) will be completed by the caregiver and/or child as appropriate.
3. Interval history will be reviewed and recorded including asthma exacerbations and adverse events.
4. Concomitant medications will be reviewed and recorded.
5. Height and weight measurements for calculation of BMI and BMI-percentile.
6. Blood for 25(OH)D level and inflammatory marker assays will be drawn by venipuncture and sent to central laboratory.
7. Urine will be obtained for calcium/creatinine ratio (all participants) and for pregnancy tests (for female participants of child-bearing potential).
8. Diary cards without the line to record Vitamin D dosing will be given to the participant/parent/guardian. These diary cards have the questions about asthma control and symptoms and asthma medications, but do not have the questions about vitamin D dosing. These will be the same cards as those given at Visit 1 (screening visit).
9. Follow-up visit for week 20 (visit 7) will be scheduled for 140 days ( $\pm 7$  days) from Study Visit 2 (baseline).

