### **Laboratory determinations of vitamin D levels**

25(OH)D levels for study endpoints will be determined at a CAP accredited and CLIA certified central laboratory. Vitamin D levels will be obtained at the local laboratory for determining inclusion criteria (25(OH)D level less than 30 ng/ml but great than 10 ng/mL) and for safety measurements at the local investigator's discretion, ensuring prompt turn around.

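### Venipuncture is mandatory at Visit 6 only for exploratory markers and has no fallback, although Table 1 accepts fingerstick for the 25(OH)D sample that decides the Part 2 endpoint

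*Combined protocol and SAP*

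**What the plan says.** - **Section 8.1.1** lets families choose between venipuncture and fingerstick for PK samples, with one exception: "Fingerstick is not an option for visits 2 and 6 since blood inflammatory markers must be assessed for those visits".
- **Section 8.1.1.1, Visit 6, item 6:** "Blood for 25(OH)D level and inflammatory marker assays will be drawn by venipuncture and sent to central laboratory". Visit 2, item 4, likewise specifies venipuncture. Neither visit has the form recording the family's preferred method, which appears at Visits 1, 3, 4 and 5, at the optional draw and at follow-up. Neither says what to do if venipuncture is declined or fails.
- **Table 1, footnote k**, attached to the central 25(OH)D row (which includes Visits 2 and 6): "blood for central laboratory vitamin D determination can be collected by venipuncture or by fingerstick using a microtainer collection tube". No visit is excepted.
- **Table 1, footnote h**, attached to the inflammatory markers: "These will be drawn by venipuncture at baseline and Visit 6".
- **Section 2.3.3** explains that fingerstick is meant to reduce anxiety about venipuncture: "We will provide the option for fingerstick collection of small volumes of blood for vitamin D level determination".
- **Status of the two measurements.** The markers serve an exploratory objective (Section 1): "Characterize selected inflammatory markers in children receiving vitamin D3 supplementation". The Part 2 endpoint (Section 3) is: "Did participants in the Part 2 active dosing cohort achieve a serum 25(OH)D of greater than or equal to 40 ng/ml at 16 weeks". Section 8.1.2 fixes the laboratory: "25(OH)D levels for study endpoints will be determined at a CAP accredited and CLIA certified central laboratory".
- **Section 9.5** counts participants who withdraw prematurely as non-responders in the primary analysis and plans multiple imputation as a sensitivity analysis. It gives no primary-analysis rule for a child who stays in the study but has no Visit 6 value.

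**The concern.** The only reason given for barring fingerstick at Visits 2 and 6 is the marker panel. The plan states no assay reason: the same central 25(OH)D sample may come from a fingerstick at Visits 3 to 5 and 7 to 9. An exploratory measurement therefore sets the condition under which the Part 2 endpoint is collected.

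A child who attends Visit 6, has taken the study drug and would give a capillary sample could leave with no endpoint value if the site follows Section 8.1.1. A site that follows footnote k would keep the value. Whether the endpoint is observed could then depend on which part of the protocol a coordinator reads. The loss would also probably not be random, since reluctance about needles plausibly varies with age. Section 5.5 itself names children's concern about blood tests as a recruitment difficulty.

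**Working it through.** **1. The passages side by side**

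| Place | Central 25(OH)D at Visits 2 and 6 | Reason given |
|---|---|---|
| Section 8.1.1 | venipuncture only | inflammatory markers |
| Section 8.1.1.1, Visit 2 item 4 and Visit 6 item 6 | venipuncture only | none |
| Table 1, footnote k | venipuncture or fingerstick | none |
| Table 1, footnote h | venipuncture, for the markers | not applicable |

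**2. The plan's own figure**

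Inputs from Section 9.2: p0 = 0.50, p1 = 0.75, one-sided 0.05, power 0.90, one-group chi-square test.

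n = [(1.645·√(0.5·0.5) + 1.282·√(0.75·0.25)) / 0.25]² = 30.35, rounded up to **31**. The stated 31 is reproduced.

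**3. Reserve in Cohort A**

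63 randomized 2:1 gives 63 × 2/3 = 42 in Cohort A. At 30% dropout, 42 × 0.70 = 29.4 remain. Keeping 31 requires dropout of no more than 1 − 31/42 = 26%. At the planned dropout there is no reserve for further missing Visit 6 values.

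**4. Effect of k lost Visit 6 samples**

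The documents give no rate of declined or failed venipuncture. I assume k = 1, 2 or 4 of 42 (2% to 10%), a true response rate of 75%, and loss unrelated to response.

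*(a) Absent samples counted as non-responses, n = 42, no other dropout.* The expected observed rate is 0.75 × (42 − k)/42. The test rejects at 27 or more responders of 42 (exact one-sided level 0.044). Exact power is P(X ≥ 27) for X binomial with 42 − k trials and probability 0.75.

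| k | Expected rate | Exact power |
|---|---|---|
| 0 | 75.0% | 0.958 |
| 1 | 73.2% | 0.933 |
| 2 | 71.4% | 0.897 |
| 4 | 67.9% | 0.777 |

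Other dropout counted as non-response would add to this. With 10% other dropout, power (normal approximation) is 0.747 before any sample is lost to the venipuncture rule and 0.577 with a further 5% lost.

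*(b) Absent samples left out (complete case), starting from the 31 evaluable that remain after 26% dropout.* Power by normal approximation is 0.906 with 31, 0.897 with 30 (5% lost) and 0.876 with 28 (10% lost). The expected rate stays at 75% if the loss is unrelated to response.

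**The case against.** **Much of the case on the other side stands.**

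- *Visit 2 acts as a filter.* Every randomized child is scheduled for venipuncture at Visit 2, and that draw is listed before drug is dispensed. A reader might picture a child who has used fingerstick throughout and is then caught out at Visit 6; under the protocol no such child exists. The exposed group is smaller: children who accepted venipuncture once and 16 weeks later decline it, or in whom it fails.
- *Loss is not certain.* Footnote k can be read as permitting fingerstick at Visit 6, and nothing forbids a second attempt within the ±7-day window. A retry helps after a failed draw but not after a refusal.
- *Instructions may exist elsewhere.* Section 8.1.2 refers specimen collection to the laboratory manual, which is not among the documents. Silence in the protocol does not prove that sites have no instruction.
- *The rule may be deliberate.* Visits 2 and 6 are the two mandatory marker visits, and Section 9.4.10 relies on that pair. A free choice of method would erode it. Footnote h also speaks of a choice at times other than baseline and Visit 6, so Table 1 could be read as agreeing with Section 8.1.1. That reading removes the contradiction but leaves the endpoint tied to the markers with no fallback.
- *Harm at Visit 2 is limited.* Section 7.2 allows replacement of participants who receive no study intervention, and Section 9.3 admits a child to the PK population with a single sample.

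None of this explains why a child who will not or cannot give venous blood at Visit 6 should also give no capillary 25(OH)D sample.

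**Conclusion.** The point holds as an inconsistency with an avoidable risk to the Part 2 endpoint. Sections 8.1.1 and 8.1.1.1 require venipuncture at Visits 2 and 6 for the sake of exploratory markers and provide no fallback. Footnote k allows fingerstick for the same 25(OH)D sample.

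A reader might infer that the rule biases the responder rate downward. The documents do not support that as stated. It follows only if absent samples in children who have not withdrawn are counted as non-responses, and Section 9.5 says this only of premature withdrawals. Under that coding, and for an assumed 1 to 4 losses of 42 with no other dropout, the expected rate falls from 75% to between 73.2% and 67.9%. Exact power falls from 0.958 to between 0.933 and 0.777. One or two losses keep power at or close to the planned 0.90; four do not. Under complete-case analysis the effect is small.

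The frequency is unknown, so these figures show sensitivity and are not a forecast. The case for acting rests on the low cost of the remedy and on the lack of reserve at the planned dropout.

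**What to change.** Reconcile Section 8.1.1, Visit 2 item 4 and Visit 6 item 6 with Table 1 footnote k, and align the laboratory manual. Suggested text:

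*Venipuncture is the planned method at Visits 2 and 6. If it is declined or unsuccessful, the 25(OH)D sample is collected by fingerstick microtainer (before the first dose at Visit 2), the inflammatory markers are recorded as not done, and the collection method is recorded.*

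State in Section 9.5 how the primary analysis treats a participant who has not withdrawn but has no Visit 6 25(OH)D value.

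The cost is a short protocol amendment; the assay and tubes are already in use at other visits. Some exploratory marker values may be lost if families decline venipuncture more readily, and wording the option as a fallback limits this. Collection methods would be mixed at the endpoint visit, as they already are at Visits 3 to 5 and 7 to 9. Recording the method allows its influence to be checked in the PK model.
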